#### **Clinical Resource Utilization**

Healthcare resource consumption									
Previous physician visits - During the past 4 weeks									
	Reimbursement								
Type of visit	Total number	Recruitment pathology- related?	NHS / public insurance	Private insurance	Out-of- pocket				
a) General practitioner		Yes □1 No □0	$\Box_1$	□ 2	□ 3				
b) Specialist		Yes □1 No □0	$\square_1$	□ 2	□ 3				

 
c) Emergency Room (without hospitalization)
 
Use of diagnostic tests and
 
	 nd specialist	Yes □1 No □0 t clinic procedur	□ 1 res - During the	2 past 4 weeks	□ 3				
	F	F							
Туре	Total number	Recruitment pathology- related?	H NHS / public insurance	Reimbursement Private insurance	Out-of- pocket				
a)		Yes □1 No □0			□ 3				
b)		Yes □1 No □0	$\Box_1$		□ 3				
c)		Yes □1 No □0			□ 3				
d)		Yes □1 No □0			□ 3				
e)		Yes □1 No □0			□ 3				
f)		Yes □1 No □0			□ 3				
g)		Yes 🗐			□ 3				

Use of care services - During the past 4 weeks							
	Total	Dogwitmont	Reimbursement				
Туре	number	pathology- related?	NHS / publi insurance	c Pi ins	rivate urance	Out-of-pocket	
		Yes 🗋			Π.		
a) Nurse home visit		No 🗋	⊔1		니 2	∐ 3	
		Yes 🗖		п			

 
b) Physiotherapy
 
		No 🖵	J ⊔1		□ 2	⊎3	
		Yes 🗖			Π.		
c) Home help		No 🖵	91		□ 2	⊎3	
A) Control to control		Yes 🗋			Π.		
d) Social transport		No 🗆			□ 2	⊎ 3	
a) Devi anna anntar		Yes 🗖					
e) Day care center		No 🗆				□ 3	
f) Other		Yes 🗋			Π.		
(specify)		No 🗖			□ 2	 	
g) Other		Yes 🗖			Π.		
(specify)	No 🖵				□ 2		
Hospital admissions - Du	iring the re	tention in the st	udy				
Admission					Reimbu	ursement	
Admission → Discharge (DD-MM- YY)	Diagnosis at discharge		Recruitme nt pathology- related?	NHS / public insuranc e	Priva insura	te Out-of- nce pocket	
			Yes 🔲 1				
//→//			No 🗆 0		2	3	
//→//			Yes 🔲 1 No 🔲 0		 2	3	
//→//			Yes 🛄 1 No 🛄 0		□ 2	3	

Т2

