#### 3.2 Secondary objectives

From a clinical perspective, secondary objectives include evaluating re-hospitalization at 60 and 90 days after discharge. Furthermore, the total number of hospitalizations the participant underwent during the whole experimentation duration will be evaluated, to stratify the outcome over a longer period and achieve a more accurate outcome in terms of predictivity and prevention. Moreover, secondary objectives include evaluation of overall health status in terms of physical performance (Short Physical Performance Battery) and quality of life (EQ Visual Analogue Scale, Short Form-12 Health Survey), as well as the evaluation of usability of the platform (System Usability Scale, Psychosocial Impact of Assistive Devices Scale) and reduction of the impact in terms of cost and resources utilizations (Qualitative Interviews). Finally, the project wants to explore the capability of the system in empowering participants in terms of digital/eHealth literacy skills achievement (eHealth Literacy Scale). From a technical perspective, secondary objectives include acquiring a pool of data derived from activity tracking to build ML models that can estimate and predict the physical condition of the patient using the proposed system.

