#### 4.2. Pilot sites description

- Italy: In Italy the end-user partner will be recruited from the Geriatrics Operating Unit of IRCCS INRCA. The research team includes multidisciplinary professional personnel that will have the possibility to meet end-users and their families to present the project and the modalities of possible participation. It will be responsibility of the research group to give technical support with the use of the TransCare technological ecosystem and take track of clinical flux of data acquired from each participant to correctly archive it and analyze it afterwards. End-users involved in pilot trial will first be screened by the appropriate physician or nurse for evaluation of clinical and physical/cognitive inclusion criteria and eventual recruitment for the TransCare project. The typical inpatient that is hospitalized in the IRCCS INRCA geriatrics department is an older adult, frail and often multi-morbid, who access the hospital for a series of conditions that fall in the acute infectious processes (urinary, biliary tract infection etc.) or cardiac sphere (chronic heart failure).
- Norway: In Norway, patients will be recruited from the municipal care services in collaboration with the local hospital (Sørlandet sykehus avd. Flekkefjord). The municipal services office serves as the single point of contact for all patients and is notified by the hospital of all potential new patients shortly after admission. The project multidisciplinary team will work closely with the municipal services office to identify and recruit patients. When a potential patient is identified, the project multidisciplinary team will meet the patient and their family to present the project. Screening for cognitive and physical inclusion criteria will be a shared responsibility between the hospital and municipal multidisciplinary teams. Home health services will provide technical training on the equipment to the patient and will also be responsible for the daily follow-up. Home health will respond to measurements and forms that trigger alarms. The typical patient receiving care in the FAR municipality is an older, frail patient with chronic illness, infections, or those requiring postoperative rehabilitation.

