The system allows the operator to only visualize if the technology is functioning and not to give an interpretation of the clinical data or send emergency alert of any kind. The system allows only the monitoring and the data collection of trends to understand the behavior and the disease trajectories over time and not real time/continuously. This is essential for research and patient data collection purposes, improving scientific knowledge on re-hospitalization and facilitating patient self-management. Thus, it is not the role of the operator to continuously monitor the data flowing through the platform, nor is it the role of the operator to promptly alert territorial health continuity services in case of emergency situations. Should the patient or his/her caregiver detect, by direct measurement or visualization on the platform, physiological parameters that may be suspect and indicators of dangerous situation, with or without the presence of symptomatology, then the patient or caregiver will be required to act as he or she would normally do, that is, to alert the appropriate medical authorities or general practitioner.

The administrator role is responsible for managing the account structure, users and devices. This role does not have access to any patient data.

Figure 4 Remote Patient Monitoring overview

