# 8 Procedure

# 8.1. Recruitment (R) and Baseline Evaluation (TO)

Recruitment and experimentation procedures are the same among the three European pilot sites. Patient will be enrolled from the operative unit/facility department, listed below:

- Geriatrics Acute Care Ward of IRCCS INRCA, in the Ancona branch, according defined inclusion criteria.
- Medical and Geriatric Departments at Sørlandet Hospital Health Trust, Flekkefjord, and the allocation of services department of municipality of Farsund according to defined inclusion criteria.
- Cardiology Department of the 'Niculae Stancioiu' Heart Institute, in Cluj-Napoca, according to the defined inclusion criteria.

During the recruitment phase (R), i.e., prior to discharge or within 3 days of discharge, general information will be collected about the subjects, particularly health status and cognitive condition. MMSE will be administered to gain a cognitive level framework, the CFS to evaluate frailty and SPPB to access physical condition.

The investigator will contact (by mail, telephone or physically) the participant to define his availability with a view to setting up the research project at home and will access his/her signed consent. When recruitment is complete, the investigator will randomize the participants into two groups: control group and experimental group. The allocation is done in an alternating randomized manner (ABAB) according to the order of inclusion of the participants. Participants in the experimental group will receive the digital platform already installed in a tablet (Table 4), or alternatively, they will use their own smartphone. In this case, they will be helped with the installation of the application and advised on how to use it. Furthermore, they will receive a set of medical/non-medical devices as reported in Table 2 and Table3. Participants in control group will not be assigned any type of technology but will simply be checked whether they will be re-hospitalized at the end of 30, 60, or 90 days.

At the staring of the experimentation, baseline evaluation (T0) is conducted directly at the hospital or at patient's home according to specific local needs of each end-user partner. The scales included Sociodemographic questionnaires, ATDPA-C, EQ-5D-5L VAS, SF-12 and eHEALS, will be administered.

The participant belonging to experimental group will receive training sessions about the digital platform and the medical/non-medical device utilization.

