#### **Clinical Resource Utilization**

Healthcare resource consumption									
Previous physician visits - During the past 4 weeks									
	Reimbursement								
Type of visit	Total number	Recruitment pathology- related?	NHS / public insurance	Private insurance	Out-of- pocket				
a) General practitioner		Yes □1 No □0	$\Box_1$	□ 2					
b) Specialist		Yes □1 No □0	$\square_1$	□ 2	□3				
c) Emergency Room (without hospitalization)					□ 3				
			Т	Reimhursement					
Туре	Total number	Recruitment pathology- related?	NHS / public insurance	Private insurance	Out-of- pocket				
a)		Yes □1 No □0	$\Box_1$		□ ₃				
b)		Yes □1 No □0	$\Box_{\mathbf{l}}$						
c)		Yes □1 No □0							
d)		Yes □1 No □0			□ 3				
e)		Yes □1 No □0			□ ₃				
f)		Yes 🗐			□ 3				
g)		Yes 🗆1 No 🗔0			□ ₃				

Use of care services - During the past 4 weeks							
	Total	Dogwitmont	Reimbursement				
Туре	number	pathology- related?	NHS / publi insurance	c Pi ins	rivate urance	Out-of-pocket	
		Yes 🗋			Π.		
a) Nurse home visit		No 🗋	⊔1		니 2	∐ 3	
		Yes 🗖		п			

 
b) Physiotherapy
 
		No 🖵	J ⊔1		□ 2	⊎3	
		Yes 🗖			Π.		
c) Home help		No 🖵	91		□ 2	⊎3	
A) Control to control		Yes 🗋			Π.		
d) Social transport		No 🗆			□ 2	⊎ 3	
a) Devi anna anntar		Yes 🗖					
e) Day care center		No 🗆				□ 3	
f) Other		Yes 🗋			Π.		
(specify)		No 🗖			□ 2	 	
g) Other		Yes 🗖			Π.		
(specify)	No 🖵				□ 2		
Hospital admissions - Du	iring the re	tention in the st	udy				
Admission					Reimbu	ursement	
Admission → Discharge (DD-MM- YY)	Diagnosis at discharge		Recruitme nt pathology- related?	NHS / public insuranc e	Priva insura	te Out-of- nce pocket	
			Yes 🔲 1				
//→//			No 🗆 0		2	3	
//→//			Yes 🔲 1 No 🔲 0		 2	3	
//→//			Yes 🛄 1 No 🛄 0		□ 2	3	

Т3

90-days Rehospitalization rate:

Yes 
No

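### The resource-use form cannot separate home visits made for TransCare from ordinary home care, so nurse home visits in the Norwegian device arm may be overstated

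*Protocol*

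**What the plan says.** Section 3.2 lists as a secondary objective the "reduction of the impact in terms of cost and resources utilizations", and section 6.2 makes resource use a secondary endpoint collected by interview.

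The instrument is the Clinical Resource Utilization form in the Appendix, which has the same layout at T1, T2 and T3. Its block headed "Use of care services - During the past 4 weeks" has seven rows, the first being "a) Nurse home visit". Each row takes a total number, a yes/no on relation to the recruitment pathology, and the payer. No field or instruction concerns contacts made for the trial.

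For Norway, section 4.2 states: "Home health services will provide technical training on the equipment to the patient and will also be responsible for the daily follow-up". It adds: "Home health will respond to measurements and forms that trigger alarms". In Italy and Romania the same section gives technical support to the research team or to technical specialists.

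This work belongs to the device arm. Section 8.1 says: "The participant belonging to experimental group will receive training sessions about the digital platform and the medical/non-medical device utilization". Of the other arm it says: "Participants in control group will not be assigned any type of technology but will simply be checked whether they will be re-hospitalized".

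**The concern.** In Norway, the service that delivers part of the intervention is also one whose visits the form can count. A visit to teach the equipment, follow up a reading or answer an alarm would be added to the same total as an ordinary nursing visit. The pathology tick does not help: a visit prompted by a heart-failure patient's weight reading is both related to the pathology and made because of the trial.

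Any such addition falls on the device arm and on one country, and it runs against an objective framed as a reduction. A real fall in ordinary home care could be masked. Because this is a question of what is captured, no later analysis of the form's totals can undo it.

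**Working it through.** The protocol gives no figure for resource use, so there is no stated number to reproduce. The check asks who is exposed, how far the mean could move, when it could move, and whether there is a comparison to distort.

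**Who is exposed.** Table 1 (section 4) gives device-arm numbers of 50 in Italy, 15 in Romania and 40 in Norway: 50 + 15 + 40 = 105. The exposed share is 40/105 = 38.1%.

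**How far the mean could move.** Let v be the number of trial-driven nurse home visits per Norwegian device patient in one 4-week window. The protocol does not give v, so it is an assumption. The Norwegian device-arm mean rises by v, and the whole device-arm mean by 40v/105.

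| v per window | Meaning | Added visits (40v) | Shift in device-arm mean |
|---|---|---|---|
| 0 | all contact remote or by other staff | 0 | 0 |
| 1 | a single visit | 40 | 0.38 |
| 4 | one visit a week | 160 | 1.52 |
| 28 | one visit every day | 1,120 | 10.67 |

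The last row is an arithmetic ceiling. The protocol speaks of daily follow-up but nowhere of a daily nurse visit, so it should not be used as an estimate.

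**When it could move.** T1, T2 and T3 fall 30, 60 and 90 days after discharge (section 4). A 28-day recall reaches back to day 30 − 28 = 2, day 60 − 28 = 32 and day 90 − 28 = 62.
- Training takes place at the start (section 8.1). Since recruitment may occur up to 3 days after discharge, training can fall inside the T1 window, but it need not. It falls outside the T2 and T3 windows.
- Use of the technology continues to days 60 and 90 (section 4), so follow-up and alarm response can fall in all three windows.

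**Whether there is a comparison to distort.** The protocol is inconsistent on whether controls complete the form:
- Section 8.1 describes control contact as a check for re-hospitalization only.
- Section 8.2 places resource use at T1 after a sentence limited to the experimental group.
- Table 5 schedules the form at T1, T2 and T3 with no restriction by arm.
- Sections 8.3 and 8.4 open with both groups and then describe the resource-use interview without naming an arm.

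Where controls complete the form, the shift above enters the between-arm difference. Where they do not, there is no such difference, but the Norwegian device-arm total still cannot be read as use of ordinary care.

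**The case against.** **The contacts may not be nurse home visits.** Section 4.2 states neither how they are made nor by which profession. Readings reach the platform through an app (section 5), and providers handle parameters and alerts through a web interface (section 5.3). Section 5 even says of the operator: "nor is it the role of the operator to promptly alert territorial health continuity services in case of emergency situations". A reader might infer that the protocol itself inflates device-arm resource use. The documents do not support that, because v = 0 is possible. This objection stands and sets the lower bound at zero. It does not remove the defect, since the form would not show which case applied. The section 5 statement also conflicts with the Norwegian description and does not settle the matter.

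**An interviewer can clarify, and sites may keep their own records.** That is possible. The form gives the interviewer no counting rule, however, and the protocol describes no separate log of these contacts. What can be said is that the split cannot be recovered from the form's totals. It cannot be said that it is unrecoverable from any source.

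**Trial-driven visits are real consumption.** They are part of the care pathway under test, and the objective names cost as well as resource use. Removing them from the comparison would favour the device arm. This stands, and it is why they should be recorded apart and reported rather than discarded.

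**The scope is small.** It is one row of seven, in one country, on a secondary endpoint. That is correct and limits the weight of the point.

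**Conclusion.** The concern holds in a limited form. The form cannot distinguish home visits made to deliver or follow up TransCare from ordinary home care, so nurse home visits in the Norwegian device arm may be overstated. The shift in the device-arm mean is 40v/105 per window, with v unknown and possibly zero; one visit a week would add 1.52. Training alone can contribute only at T1.

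Two stronger readings are not supported. One is that inflation is certain: the mode of contact is not stated. The other is that the comparison between arms is biased at every visit: that requires control data, which sections 8.1 and 8.2 put in doubt.

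The conclusion rests on the form being used as printed and on some Norwegian follow-up taking place as nurse visits at home. It is a cheap improvement to a secondary endpoint, best made before data collection, and it does not touch the primary endpoint.

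**What to change.** - On all three forms, add a separate row for contacts made for TransCare (training, technical help, follow-up of measurements, alarm response). Add an instruction to count them there instead of in the ordinary-care rows.
- Report resource use both without and with these contacts, and show Norway separately. The first describes ordinary care; the second includes what delivering the intervention consumes.
- State how the Norwegian contacts are made (home visit, telephone or remote) and by whom.
- Reconcile sections 8.1 and 8.2 with Table 5 and sections 8.3 and 8.4 on whether controls complete the form, and at which visits.
- Reconcile section 4.2 (Norway) with section 5 on follow-up and alarms.

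The cost is one row and one instruction line on three forms, and about a minute of staff time per visit. The reconciliations are changes of text only, unless they add control-arm interviews that are not now planned.

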#### 60-days Rehospitalization rate:

#### Short Physical Performance Battery

#### 1. Repeated Chair Stands

Instructions: Please **stand up straight as quickly as you can five times, without stopping in between**. After standing up each time, sit down and then stand up again. Keep your arms folded across your chest. Please watch while I demonstrate. I'll be timing you with a stopwatch. Are you ready?

Begin Grading: **Begin stop watch when subject begins to stand up**. Count aloud each time subject arises. **Stop the stopwatch when subject has straightened up completely for the fifth time**. Also stop if the subject uses arms, or after 1 minute, if subject has not completed rises, and if concerned about the subject's safety. Record the number of seconds and the presence of imbalance.

- Time: \_\_sec (if five stands are completed)
- Number of Stands Completed: 1234

5 Chair Stand Ordinal Score:

- 0 = unable
- 1 = > 16.7 sec
- 2 = 16.6-13.7 sec
- 3 = 13.6-11.2 sec
- 4 = < 11.1 sec

#### 2. Balance Testing

Begin with a **semitandem stand** (heel of one foot placed by the big toe of the other foot). Individuals unable to hold this position should try the side-by-side position. Those able to stand in the semitandem position should be tested in the full tandem position. Once you have completed time measures, complete ordinal scoring.

#### a. Semitandem Stand

Instructions: Now I want you to try to stand with the **side of the heel of one foot touching the big toe of the other foot for about 10 seconds**. You may put either foot in front, whichever is more comfortable for you. Please watch while I demonstrate. Grading: Stand next to the participant to help him or her into

semitandem position. Allow participant to hold onto your arms to get balance. Begin timing when participant has the feet in position and let's go.

- 2 = Held for 10 sec
- 1 = Held for less than 10 sec; (number of seconds held: \_\_\_\_\_sec)
- 0 = Not attempted

#### b. Side-by-Side stand

Instructions: I want you to try to **stand with your feet together**, **side by side**, **for about 10 sec**. Please watch while I demonstrate. You may use your arms, bend your knees, or move your body to maintain your balance, but try not to move your feet. Try to hold this position until I tell you to stop. Grading: Stand next to the participant to help him or her into the side-by-side position. Allow participant to hold onto your arms to get balance. Begin timing when participant has feet together and let's go.

- 2 = Held of 10 sec
- 1 = Held for less than 10 sec; (number of seconds held: \_\_\_\_\_ sec)
- 0 = Not attempted

#### 3. Tandem Stand

Instructions: Now I want you to try to **stand with the heel of one foot in front of and touching the toes of the other foot for 10 sec**. You may put either foot in front, whichever is more comfortable for you. Please watch while I demonstrate.

Grading: Stand next to the participant to help him or her into the side-by-side position. Allow participant to hold onto your arms to get balance. Begin timing when participant has feet together and let's go.

- 2 = Held of 10 sec
- 1 = Held for less than 10 sec; (number of seconds held: \_\_\_\_\_ sec)
- 0 = Not attempted

Balance Ordinal Score:

• 0 = side by side 0-9 sec or unable

- 1 = side by side 10, <10 sec semitandem
- 2 = semitandem 10 sec, tandem 0-2 sec
- 3 = semitandem 10 sec, tandem 3-9 sec
- 4 = tandem 10 sec

#### 4. 8' Walk (2.44 meters)

Instructions: This is our walking course. If you use a cane or other walking aid when walking outside your home, please use it for this test. I want you to walk at your usual pace to the other end of this course (a distance of 8'). Walk all the way past the other end of the tape before you stop. I will walk with you. Are you ready? Grading: Press the start button to start the stopwatch as the participant begins walking. **Measure the time** take to walk 8'. Then complete ordinal scoring.

Time: sec

Gait Ordinal Score:

- 0 = could not do
- 1 = >5.7 sec (<0.43 m/sec)
- 2 = 4.1-6.5 sec (0.44-0.60
- m/sec)
- 3 = 3.2-4.0 (0.61-0.77 m/sec)
- 4 = <3.1 sec (>0.78 m/sec)

**Summary Ordinal Score**: Range: 0 (worst performance) to 12 (best performance). Shown to have predictive validity showing a gradient of risk for mortality, nursing home admission, and disability.

Visual Analogic Scale (VAS)

#### **Clinical Resource Utilization**

Healthcare resource consumption									
Previous physician visits - During the past 4 weeks									
	Reimbursement								
Type of visit	Total number	Recruitment pathology- related?	NHS / public insurance	Private insurance	Out-of- pocket				
a) General practitioner		Yes □1 No □0	$\Box_1$	□ 2					
b) Specialist		Yes □1 No □0	$\square_1$	□ 2	□3				
c) Emergency Room (without hospitalization)					□ 3				
			Т	Reimhursement					
Туре	Total number	Recruitment pathology- related?	NHS / public insurance	Private insurance	Out-of- pocket				
a)		Yes □1 No □0	$\Box_1$		□ ₃				
b)		Yes □1 No □0	$\Box_{\mathbf{l}}$						
c)		Yes □1 No □0							
d)		Yes □1 No □0			□ 3				
e)		Yes □1 No □0			□ ₃				
f)		Yes 🗐			□ 3				
g)		Yes 🗆1 No 🗔0			□ ₃				

Use of care services - During the past 4 weeks							
	Total	Dogwitmont	Reimbursement				
Туре	number	pathology- related?	NHS / publi insurance	c Pi ins	rivate urance	Out-of-pocket	
		Yes 🗋			Π.		
a) Nurse home visit		No 🗋	⊔1		니 2	∐ 3	
		Yes 🗖		п			

 
b) Physiotherapy
 
		No 🖵	J ⊔1		□ 2	⊎3	
		Yes 🗖			Π.		
c) Home help		No 🖵	91		□ 2	⊎3	
A) Control to control		Yes 🗋			Π.		
d) Social transport		No 🗆			□ 2	⊎ 3	
a) Devi anna anntar		Yes 🗖					
e) Day care center		No 🗆				□ 3	
f) Other		Yes 🗋			Π.		
(specify)		No 🗖			□ 2	 	
g) Other		Yes 🗖			Π.		
(specify)	No 🖵				□ 2		
Hospital admissions - Du	iring the re	tention in the st	udy				
Admission					Reimbu	ursement	
Admission → Discharge (DD-MM- YY)	Diagnosis at discharge		Recruitme nt pathology- related?	NHS / public insuranc e	Priva insura	te Out-of- nce pocket	
			Yes 🔲 1				
//→//			No 🗆 0		2	3	
//→//			Yes 🔲 1 No 🔲 0		 2	3	
//→//			Yes 🛄 1 No 🛄 0		□ 2	3	

Т3

90-days Rehospitalization rate:

Yes 
No

